### **11.3 Exploratory Objectives**

There are two exploratory objectives for this study.

- a) The first exploratory objective (EO 1) is to compare the proportion of death, by EHR-based prognostic decision support or usual care.

The analysis is similar to secondary objective 2 though the proportion of death is the outcome.

- b) The second exploratory objective (EO 2) is to compare hospital length of stay among hospitalized children, by EHR-based prognostic decision support or usual care.

The Wilcoxon rank-sum test will be used to compare length of stay between intervention and control arms.

A cox regression model will be conducted. The outcome is length of stay. The covariates under the consideration will be similar to the ones listed in the primary objective analysis 11.1.

## Appendix 1

Prior B-lactam	Severe PCN allergy	Moderate to large PPE	Necrotizing or severe pneumonia	Aspiration	Outpatient	Inpatient	ICU without invasive mechanical ventilation or shock	ICU WITH invasive mechanical ventilation and without shock	ICU WITH invasive mechanical ventilation AND shock
NO	NO	NO	NO	NO	Amoxicillin	Ampicillin	Ampicillin or Ceftriaxone	Ceftriaxone	Ceftriaxone plus Vancomycin
NO	NO	NO	NO	YES	Amoxicillin/Clavulanate	Ampicillin/Sulbactam	Ampicillin/Sulbactam or Clindamycin	Ampicillin/Sulbactam or Clindamycin	Ceftriaxone plus Vancomycin
NO	NO	NO	YES	NO	n/a	Ceftriaxone plus Clindamycin or Vancomycin	Ceftriaxone plus Clindamycin or Vancomycin	Ceftriaxone plus Vancomycin	Ceftriaxone plus Vancomycin
NO	NO	NO	YES	YES	n/a	Ceftriaxone plus Clindamycin or Vancomycin	Ceftriaxone plus Clindamycin or Vancomycin	Ceftriaxone plus Vancomycin	Ceftriaxone plus Vancomycin
NO	NO	YES	NO	NO	n/a	Ampicillin	Ceftriaxone plus Clindamycin or Vancomycin	Ceftriaxone plus Clindamycin or Vancomycin	Ceftriaxone plus Vancomycin
NO	NO	YES	NO	YES	n/a	Ampicillin/Sulbactam	Ceftriaxone plus Clindamycin or Vancomycin	Ceftriaxone plus Clindamycin or Vancomycin	Ceftriaxone plus Vancomycin
NO	NO	YES	YES	NO	n/a	Ceftriaxone plus Clindamycin or Vancomycin	Ceftriaxone plus Clindamycin or Vancomycin	Ceftriaxone plus Vancomycin	Ceftriaxone plus Vancomycin
NO	NO	YES	YES	YES	n/a	Ceftriaxone plus Clindamycin or Vancomycin	Ceftriaxone plus Clindamycin or Vancomycin	Ceftriaxone plus Vancomycin	Ceftriaxone plus Vancomycin

NO	YES	NO	NO	NO	Clindamycin	Clindamycin	Clindamycin or Levofloxacin	Levofloxacin	Levofloxacin plus Vancomycin
NO	YES	NO	NO	YES	Clindamycin	Clindamycin	Clindamycin or Levofloxacin	Levofloxacin	Levofloxacin plus Vancomycin
NO	YES	NO	YES	NO	n/a	Levofloxacin plus Clindamycin or Vancomycin	Levofloxacin plus Clindamycin or Vancomycin	Levofloxacin plus Vancomycin	Levofloxacin plus Vancomycin
NO	YES	NO	YES	YES	n/a	Levofloxacin plus Clindamycin or Vancomycin	Levofloxacin plus Clindamycin or Vancomycin	Levofloxacin plus Vancomycin	Levofloxacin plus Vancomycin
NO	YES	YES	NO	NO	n/a	Clindamycin	Levofloxacin plus Clindamycin or Vancomycin	Levofloxacin plus Clindamycin or Vancomycin	Levofloxacin plus Vancomycin
NO	YES	YES	NO	YES	n/a	Clindamycin	Levofloxacin plus Clindamycin or Vancomycin	Levofloxacin plus Clindamycin or Vancomycin	Levofloxacin plus Vancomycin
NO	YES	YES	YES	NO	n/a	Levofloxacin plus Clindamycin or Vancomycin	Levofloxacin plus Clindamycin or Vancomycin	Levofloxacin plus Vancomycin	Levofloxacin plus Vancomycin
NO	YES	YES	YES	YES	n/a	Levofloxacin plus Clindamycin or Vancomycin	Levofloxacin plus Clindamycin or Vancomycin	Levofloxacin plus Vancomycin	Levofloxacin plus Vancomycin
YES	NO	NO	NO	NO	Amoxicillin or Amoxicillin/Clavulanate	Ampicillin or Ceftriaxone	Ampicillin or Ceftriaxone	Ceftriaxone	Ceftriaxone plus Vancomycin
YES	NO	NO	NO	YES	Amoxicillin/Clavulanate or Clindamycin	Ampicillin/Sulbactam or Clindamycin	Ampicillin/Sulbactam or Clindamycin	Ampicillin/Sulbactam or Clindamycin	Ceftriaxone plus Vancomycin

YES	NO	NO	YES	NO	n/a	Ceftriaxone plus Clindamycin or Vancomycin	Ceftriaxone plus Clindamycin or Vancomycin	Ceftriaxone plus Vancomycin	Ceftriaxone plus Vancomycin
YES	NO	NO	YES	YES	n/a	Ceftriaxone plus Clindamycin or Vancomycin	Ceftriaxone plus Clindamycin or Vancomycin	Ceftriaxone plus Vancomycin	Ceftriaxone plus Vancomycin
YES	NO	YES	NO	NO	n/a	Ampicillin or Ceftriaxone	Ceftriaxone plus Clindamycin or Vancomycin	Ceftriaxone plus Clindamycin or Vancomycin	Ceftriaxone plus Vancomycin
YES	NO	YES	NO	YES	n/a	Ampicillin/Sulbactam or Clindamycin	Ceftriaxone plus Clindamycin or Vancomycin	Ceftriaxone plus Clindamycin or Vancomycin	Ceftriaxone plus Vancomycin
YES	NO	YES	YES	NO	n/a	Ceftriaxone plus Clindamycin or Vancomycin	Ceftriaxone plus Clindamycin or Vancomycin	Ceftriaxone plus Vancomycin	Ceftriaxone plus Vancomycin
YES	NO	YES	YES	YES	n/a	Ceftriaxone plus Clindamycin or Vancomycin	Ceftriaxone plus Clindamycin or Vancomycin	Ceftriaxone plus Vancomycin	Ceftriaxone plus Vancomycin

## Appendix 2

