2.0 Rationale and Study Phases

Extensive variation in both antibiotic use and hospitalization decisions is evident among clinicians caring for children with pneumonia, with high potential for avoidable harm. In our prior study, one-third of children were hospitalized for less than 48 hours and nearly 10% less than 24 hours. Some of these hospitalizations were likely unnecessary. Most of these children also received broad-spectrum antibiotic therapy instead of the narrow-spectrum agents recommended by the national guideline. Conversely, one-third of children admitted to intensive care were initially managed on a general ward—earlier transfer for more intensive therapy may have improved outcomes for some of these children. New strategies to inform decision making are needed, and the combination of risk stratification using objective tools and clinical decision support in the ED setting are innovative and promising approaches to achieve this goal.

Phase 1: *To test the hypothesis that electronic antibiotic decision support increases guideline-concordant antibiotic use compared with usual care in the ED.*

The primary outcome is the proportion of children exclusively receiving guideline-concordant 1st line antibiotic therapy during the first 24 hours of care (Table 1). Secondary outcomes include exclusive use of concordant antibiotic therapy for the entire episode, any use of concordant antibiotic therapy during the first 24 hours of care and for the entire episode, and ED revisits and hospitalizations within 72 hours and 7 days of the index discharge.

Phase 2: *To test the hypothesis that the delivery of severity information generated by our prognostic tool leads to more appropriate site of care disposition compared to usual care.*

The primary outcome is appropriate site of care disposition (Table 2). Surveillance for subsequent ED visits and hospitalizations to our institutions as well as escalation to higher levels of care will be captured within the EHR data extracted by the decision support application. Secondary efficacy and safety outcomes include the overall site of care disposition (ED discharge, ward, ICU), and ED revisits and hospitalizations within 72 hours and 7 days of the index discharge.

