7.5 Outcomes (P2)

The primary outcome is appropriate site of care disposition (Table 2). Surveillance for subsequent ED visits and hospitalizations to our institutions as well as escalation to higher levels of care will be captured within the EHR data extracted by the decision support application. To adjudicate the appropriateness of brief hospitalizations and ICU stays (<24 hours), an investigator in both Nashville and Pittsburgh will review all hospitalizations meeting these criteria, blinded to intervention assignment.

Secondary efficacy and safety outcomes include the overall site of care disposition (ED discharge, ward, ICU), and ED revisits and hospitalizations within 72 hours and 7 days of the index discharge.

Exploratory outcomes include death, and for those hospitalized at the index visit, hospital length of stay.

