#### **3.3 Exploratory**

- a) EO 1: To compare the proportion of death, by EHR-based prognostic decision support or usual care.
- b) EO 2: To compare hospital length of stay among hospitalized children, by EHR-based prognostic decision support or usual care.

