### **11.1 Primary Objective**

The primary objective (PO 1) of the study is to compare proportions of appropriate overall site of care disposition with or without EHR-based prognostic decision support in children 0.6-17 years of age presenting for emergency care. The hypothesis for this primary objective is that the proportion of appropriate site of care disposition is higher in the group receiving EHR-based prognostic decision support vs. the group receiving usual care. This information is captured through chart review and entered in the REDCap database. An investigator in both Nashville and Pittsburgh will be in charge of outcome assessment review, blinded to intervention assignment, and will decide whether site of care disposition is appropriate, yes (1) or no (0), based on Appendix 2 table for this analysis.

The proportions will be compared between the intervention arm versus the control arm using a Cochran-Mantel-Haenszel method in a stratified analysis by site to control for two sites at the alpha 0.05 level. The proportion difference and corresponding 95% confidence interval for concordance of antibiotics with or without adjusting for sites will also be calculated.

We will conduct a multivariable logistic regression model to compare appropriate site of care disposition between the two study arms, controlling for important baseline covariates. Important baseline covariates (e.g., age, sex, race, site, season, month, frequency of bacteremia and other pneumonia-related complications) will also be assessed and included as model covariates. Robust standard errors will be calculated to account for hospital clustering effects. We will also perform analyses to assess for interactions between two study arms and predicted risk for severe outcomes, age, provider type, and initial site of care, to identify subgroups in whom decision support may be most useful.

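### Phase 2 tests length of stay only in hospitalised children, a group formed after allocation by the decision the tool targets, so the comparison is not randomised and can mislead in either direction

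*SAP*

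**What the plan says.** SAP 3.3 sets the objective: "To compare hospital length of stay among hospitalized children". SAP 5.3 and 11.3 keep the same restriction. Protocol 7.5 lists the outcome "for those hospitalized at the index visit, hospital length of stay", which ties it to the index admission.

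SAP 11.3 plans two analyses on that subset. The first is a rank test by arm ("The Wilcoxon rank-sum test will be used to compare length of stay between intervention and control arms"). The second is a model: "A cox regression model will be conducted. The outcome is length of stay". The model's covariates are to resemble those of SAP 11.1, which are introduced as "Important baseline covariates (e.g., age, sex, race, site, season, month, frequency of bacteremia and other pneumonia-related complications".

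SAP 6.3.2 assigns the arm when the treating provider confirms pneumonia and eligibility, before the child's disposition is settled. The Phase 2 hypothesis in Protocol 2.0 is that "delivery of severity information generated by our prognostic tool leads to more appropriate site of care disposition compared to usual care". SAP 8.1 makes intention-to-treat the default population unless stated otherwise. Neither document plans a length-of-stay analysis in all randomised children, a sensitivity analysis for selection into hospital, or a caution on interpretation.

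**The concern.** Being hospitalised is a consequence of the decision that the tool informs. Conditioning on it compares children admitted with the tool against children admitted without it, and randomisation no longer makes those groups alike.

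The plan itself gives reason to expect a difference. Under Protocol Table 2 and SAP Appendix 2, a ward stay under 24 hours without objective criteria is inappropriate, while home care with no hospitalisation in the next 24 hours is appropriate. One success that the primary outcome rewards is therefore the removal of the shortest stays from the length-of-stay set. Protocol 8.6 foresees the opposite shift, more admissions of low-risk children.

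In the first case, a finding of longer stay could sit beside a positive primary result and be read as harm. In the second, a finding of shorter stay could be read as benefit although hospital use had risen.

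**Working it through.** **The plan's own figures.** No effect size or power is stated for length of stay. The only Phase 2 sample-size figure (SAP 6.2.2: 1000 per arm, 90% against 93.4%, 80% power) concerns the primary outcome. It reproduces closely: two-sided power is 78.7%, and 80% power corresponds to 3.45 points. Only the 1000 per arm is used below.

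**Inputs from the documents.** In the earlier study cited in SAP 6.1, nearly 10% of hospitalised children stayed under 24 hours and one-third under 48 hours. Admission rates at the two sites are not given. The median and range across US children's hospitals in Protocol 1.0 (31%; 19% to 69%) serve as assumptions.

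**Step 1: rank effect, no distribution needed.** Let a share *a* of the under-24-hour stays be averted, with no other stay changed. On the control-arm rank scale, the short stays occupy 0 to 0.10 (mean rank 0.05) and the rest 0.10 to 1 (mean rank 0.55). Then

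P(intervention stay > control stay) = [(1 − a) × 0.10 × 0.05 + 0.90 × 0.55] / (1 − 0.10a)

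- a = 0.5: (0.0025 + 0.495) / 0.95 = 0.524
- a = 1: 0.495 / 0.90 = 0.55

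Both exceed 0.5, although hospital use has fallen.

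**Step 2: the reverse case.** If the tool adds short admissions equal to a share *b* of admissions, and they are distributed like the existing under-24-hour stays, P = (0.5 + 0.05b) / (1 + b). This gives 0.5025 / 1.05 = 0.479 for b = 0.05 and 0.505 / 1.10 = 0.459 for b = 0.10. Stay now looks shorter, although use has risen.

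**Step 3: effect on the mean.** Assume mean stays of 0.75, 1.5 and 3.5 days for the under-24-hour, 24–48-hour and longer groups. The mean is 0.10 × 0.75 + 0.2333 × 1.5 + 0.6667 × 3.5 = 2.758 days. Averting half of the short stays gives (2.758 − 0.0375) / 0.95 = 2.864 days, a rise of 0.11 day (3.8%). Bed-days fall by 0.0375 / 2.758 = 1.4%.

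**Step 4: what the planned tests would report.** A lognormal stay was fitted to the two shares (median 68.2 h, mean 95.0 h, log-SD 0.815), and 1500 trials were simulated per setting with 1000 children per arm.

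| Under-24 h stays averted | Median stay, control vs intervention | Unadjusted Cox HR for discharge | Wilcoxon significantly longer, at 19 / 31 / 69% admitted |
|---|---|---|---|
| Half | 68.2 vs 71.8 h | about 0.95 | 11 / 18 / 31% |
| All | 68.2 vs 75.5 h | about 0.90 | 38 / 54 / 88% |

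**Step 5: the same scenarios in all randomised children, zero hours if never hospitalised.** With all short stays averted, expected hours per child fall from 18.1 to 17.7, from 29.5 to 28.9 and from 65.6 to 64.4 at 19%, 31% and 69% admitted. The direction is now right. The rank test reports a significantly longer stay in 0.1% to 0.8% of trials.

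Precision is poor. For a lognormal, E(X²) = 95.0² × exp(0.815²), about 17,530. At 31% admitted, the variance per child is 0.31 × 17,530 − 29.45² ≈ 4,567, so the SE of the difference in means is √(2 × 4,567 / 1000) ≈ 3.0 h. The same formula gives 2.45 h at 19% and 3.95 h at 69%. The true reduction is only 0.16 h (19% admitted, half averted) to 1.18 h (69%, all averted). By a normal approximation the estimated mean difference has the wrong sign in 38% (1.18 / 3.95 = 0.30 SE) to 47% (0.16 / 2.45 = 0.07 SE) of trials. The all-randomised rank test rejects in about 7% to 20%.

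**The case against.** **Low stakes.** This is one of two exploratory Phase 2 objectives, with no power claim and no alpha adjustment (SAP 7.2). A reader might infer that the defect undermines Phase 2. It does not: no decision rule or primary result depends on it. This stands.

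**Existing mitigation.** A reader might infer that only a crude test is planned. The same paragraph of SAP 11.3 adds a Cox model. Its covariate list is given as examples, so severity could be included, and SAP 11.1 already uses predicted risk as an interaction variable. Protocol 7.5 and SAP 6.1.2 also list overall disposition (ED discharge, ward, ICU) as a secondary outcome, which would show a shift in who is admitted. These points help but do not settle the matter. Neither predicted risk nor presenting severity is named as an adjustment covariate, and adjustment cannot be relied on to restore a randomised comparison. The first secondary objective in SAP 3.2, 5.2 and 11.2 is worded as appropriate disposition, so the distribution itself is not clearly carried into the analysis.

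**Direction.** A reader might infer that a beneficial tool will look harmful. The documents do not support a fixed sign. Protocol 8.6 allows for more low-risk admissions, and better ward or ICU placement could truly change stay.

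**The remedy.** Counting index hours only would give zero, the best score, to a child sent home and admitted soon afterwards. Deaths would have no defined value in a difference of means. An all-randomised comparison is also imprecise, and with 31% to 81% zeros its rank test is largely a test of admission. The first two faults are avoidable by definition. The third is a real cost. A one-sentence caution would be a cheaper alternative, but it would leave a non-randomised test as the only between-arm comparison.

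**Conclusion.** The concern holds as a minor point about an exploratory outcome. The planned Wilcoxon and Cox comparisons condition on a post-allocation event that the tool targets. They are not randomised comparisons, and their sign can oppose the true effect on hospital use, in either direction.

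The rank probabilities of 0.524 and 0.55 rest only on the 10% share, the fraction averted and no other stay changing. The medians, hazard ratios and rejection rates also depend on the assumed admission rates and the fitted lognormal. Averting every short stay is an upper bound, because some short stays meet objective criteria and count as appropriate. The 38% to 88% figures should therefore not be read as expected error rates.

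**What to change.** In SAP 3.3, 5.3 and 11.3, with Protocol 7.5 aligned:

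- Make the between-arm comparison total hospital hours in all randomised children, from the index ED visit through 7 days after index discharge. Count the hours of any hospitalisation in that window, so that a child sent home and then admitted is not scored zero. Score zero only for children never hospitalised.
- Use a rank test stratified by site, with deaths given the worst rank.
- Add a difference in mean hours with a robust or bootstrap confidence interval. Deaths contribute their observed hours and are reported alongside under the first exploratory objective.
- Report length of stay among the hospitalised descriptively, beside the distribution of disposition by arm, with a statement that it is conditional on admission.

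The cost is SAP wording. Visit times and readmissions are already to be collected (SAP 7.1), and the 7-day horizon matches an existing secondary outcome, including its limit to admissions at the participating institutions. The downside is many zeros and low power, so the result will be imprecise and should be described as such.

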### Appropriate Site of Care Definitions

Disposition	Appropriate if:
Home care	No subsequent hospitalization within 24h
Inpatient, ward	Hospital length of stay $\geq$ 24h; or hospital length of stay $<$ 24h but objective criteria for admission present (eg, need for supplemental oxygen); and no subsequent transfer to ICU within 24h
Inpatient, ICU	ICU length of stay $\geq$ 24h; or ICU length of stay $<$ 24h but objective criteria for ICU admission present (eg, respiratory failure)
